2.1.2 Sample Size

Since no formal hypothesis will be tested, there is no statistical justification of sample size.

Peripheral pulmonary lesions vary in their location in the tracheobronchial tree, their size, and their characteristics (e.g., concentric vs. eccentric). A sample size of 5-10 subjects per site allows greater potential to evaluate the usability and performance of the system for visualization and sampling this range of lesions.

Performance feedback for this traditional feasibility study is sought from more than 1 physician. While staying within the sample size confines of a traditional feasibility study, Boston Scientific has elected to seek the expertise of 2 to 3 interventional bronchoscopists.

2.1.3 Statistical Methods

For the primary endpoint of clinical success, the analysis will be performed as described below.

For all PP patients, the primary endpoint of clinical success occurs when there is at least one adequate specimen of cellular matter suitable for the cytologic evaluation of targeted lung lesions is acquired under real-time visualization by the iNod System. If there is no adequate specimen of cellular matter suitable for the cytologic evaluation of targeted lung lesions, under real-time visualization by the iNod System, then the patient will be considered a clinical failure. The primary endpoint will be evaluated as the number of clinical successes out of all PP patients; a 95% exact confidence interval will also be calculated for the primary endpoint.

For patients who do not have clinical success and a salvage procedure is done, the proportion of patients with a salvage procedure for which at least one adequate specimen of cellular matter suitable for the cytologic evaluation of targeted lung lesions will be calculated; a 95% exact

Boston Scientific
iNod Feasibility SAP
91154618 Rev/Ver AA
Page 5 of 11

confidence interval will also be calculated for the proportion of patients with a successful salvage procedure.

3 GENERAL STATISTICAL METHODS

3.1 Description of Statistical Methods

Descriptive statistics will be presented for all intent-to-treat (ITT) and per-protocol (PP) patients. The mean (\pm standard deviation) will be used to describe continuous variables with a normal distribution and the median (and interquartile range) will be used to describe continuous variables with a skewed distribution. Frequency tables will be used to summarize discrete variables. Proportions of patients with adverse events and SAEs will be reported. No hypothesis testing will be performed.

3.2 Analysis Sets

3.2.1 Intent-to-Treat Cohort

The intent-to-treat (ITT) cohort consists of subjects enrolled in the study regardless of whether a specimen was obtained from the iNod System. The point of enrollment is the time at which, following recruitment, a subject signs and dates the informed consent form.

3.2.2 Per Protocol Cohort

The per-protocol (PP) cohort is a subset of the ITT subjects for whom a specimen was obtained using the iNod System.

3.2.3 Restricted Per Protocol Cohort

The restricted per-protocol (rPP) cohort is a subset of the PP subjects for whom the ICF was executed properly and all eligibility criteria were met.

3.3 Control of Systematic Error/Bias

All subjects who have met the inclusion/exclusion criteria and have signed the ICF will be eligible for enrollment in the study. Visual and/or electronic data review will be performed to identify possible data discrepancies. Manual and/or automatic queries will be created in the EDC system and will be issued to the site for appropriate response. Site staff will be responsible for resolving all queries in the database.

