Pulmonary lesions are a common but difficult issue for primary care and specialty physicians and are often found incidentally on Chest X-Ray (CXR) or Computed Tomography (CT) scan.⁴ With the results of the National Lung Cancer Screening Trial demonstrating a reduction in lung cancer mortality with screening of high risk patients with low dose CT scan, the number of nodules detected requiring follow up is likely to increase exponentially as 25% of those screened had a detected lung abnormality.⁵ In studies of incidentally detected nodules, the prevalence of malignancy ranges from 2-82%.⁶ The problem for clinicians is deciding on the management and further diagnostic modalities to pursue.

The various recommended procedures for obtaining tissue diagnosis in these intermediate cases include transthoracic needle aspiration (TTNA), surgery, and flexible bronchoscopy (FB). The diagnostic yield with FB varies with lesion size and location. A lesion having a bronchus sign (the finding of a CT-visible bronchus leading to the lesion) increases the success of transbronchial biopsy and brushing.⁷ [ENREF 7](#) The ACCP recommends that nodules without a CT-bronchus sign should be pursued with TTNA unless radial endobronchial ultrasound (R-EBUS) is available.⁸ [ENREF 6](#) Bronchoscopy is commonly used for pulmonary masses, but the yield, while high, does not approach 100%.

Endobronchial ultrasound (EBUS) and radial EBUS (R-EBUS) are known to be safe and effective imaging techniques for transbronchial and endobronchial biopsy.^{9, 10} The location of the bronchoscope at the lesion can be verified with real-time visualization with the guide sheath acting as an extended working channel to maintain the location during R-EBUS

biopsy. Increased use of screening CT scans has led to the increased detection of pulmonary lesions and nodules.

The intent of this clinical study is to demonstrate feasibility to visualize, access, and obtain specimens adequate for cytology of lung lesions in subjects with suspected lung cancer when using the iNod System.

2. Device Description

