7.2. Withdrawal

All subjects enrolled in the clinical study (including those withdrawn from the clinical study or lost to follow-up) shall be accounted for and documented. If a subject withdraws from the clinical investigation, the reason(s) shall be reported. If such withdrawal is due to problems related to investigational device safety or performance, the investigator shall ask for the subject's permission to follow his/her status/condition outside of the clinical study.

Reasons for withdrawal include physician discretion, subject choice to withdraw consent, loss to follow-up and death. Subjects may withdraw from the study at any time, with or without reason, and without prejudice to further treatment. All applicable case report forms up to the point of subject withdrawal must be completed. Additional data may no longer be collected after the point at which a subject has been withdrawn from the study or withdraws his/her consent, for whatever reason. All open adverse events should be

Confidential

closed or documented as chronic. Data collected up to the point of subject withdrawal may be used.

Subjects withdrawn prior to undergoing the diagnostic procedure with the iNod System will not count toward a center's 10 subject limit.

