8.1. Data Collection

Boston Scientific
iNod Feasibility Clinical Protocol
91122035 Rev/Ver AA
Page 18 of 44

Table 8.1-1: Data Collection Schedule

Procedure/Assessment	Study-Specific (iNod) or Standard of Care (SOC)	Screening	Baseline	Procedure	Completion / Study Exit
Informed consent form, including informed consent signature date	iNod		X		
Demographics, including date of birth, and gender	iNod		X		
Physical Exam	iNod				
HCG Pregnancy Testing for women of childbearing potential	iNod		X		
Historic Diagnostic Chest CT	SOC	X			
Confirmed at enrollment, but per standard of care within 6 weeks of procedure					
Historic PET Results	SOC	O			
Medical history	iNod		X		
Sedation	SOC			X	
iNod System Diagnostic Procedure(s)	iNod			X	
iNod Ultrasound (US) Images including lesion visualization and needle visualized in the iNod US Field	iNod			X	
Fluoroscopic Images during iNod Maneuver(s)	iNod			O	
ROSE (Rapid on-site Evaluation) of obtained specimen (s)	SOC			X	
Complete Cytology of obtained specimen(s)	SOC			X	X
Standard of Care Diagnostic Procedures (as indicated as required)	SOC			O	
Standard of Care US Images including lesion visualization and needle visualized in the iNod US Field	SOC			X	
Fluoroscopic Images during Standard of Care Maneuver(s)	SOC			O	
ROSE (Rapid on-site Evaluation) of obtained specimen (s)	SOC			X	
Complete Cytology of obtained specimen(s)	SOC			X	X
Discharge X-ray	SOC				X
Device, Procedure, and Anesthesia-related adverse events assessment, including Day-7 Post-Procedure Call	iNod			X	X

X = required; O = optional but recommended

Boston Scientific
 iNod Feasibility Clinical Protocol
 91122035 Rev/Ver AA
 Page 19 of 44

8.2. *Study Candidate Screening*

Potential study candidates will be selected based on the investigator's review of subject referrals for evaluation of their medical history and assessment of candidate's Chest CT, completed within 6 weeks of study procedure, that indicate the presence of a suspected solid peripheral pulmonary nodule between 1cm and 7cm in size.

Only subjects that meet the CT and all other Inclusion Criteria should move forward to the Informed Consent process. All subjects screened and consented will be patients of the investigator(s).

8.3. *Informed Consent*

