Written Informed Consent must be obtained for all subjects who are potential study candidates. Subjects will be asked to sign the Informed Consent form before any study-specific tests or procedures are performed. The Informed Consent form is study-specific and must be approved by the study Institutional Review Board (IRB)/Ethics Committee (EC) and Competent Authority, as applicable.

8.4. *Baseline*

Must be conducted no more than 2 weeks before or on the day of (preceding) iNod System procedure.

- Informed Consent
- Eligibility Criteria Assessment
- Demographics
- Bronchoscopy History
- Physical Exam including Height & Weight
- Confirmation of a peripheral pulmonary lesion, per historic Chest CT (within 6 weeks of procedure)

Baseline attributes of the target lesion will be recorded:

- Location of Lesion
- Size of Lesion
- Attributes of Lesion (e.g. solid or partial ground glass)

8.5. *iNod Diagnostic Procedure*

The subject will be prepared for the study procedure under sedation as per current standard of care.

The investigator will perform a bronchoscopic assessment of all lobes of the lung and confirm that there are no contraindications to continue with the iNod System procedure.

iNod System components are supplied to the investigative centers for the conduct of this clinical study by Boston Scientific, free of charge. Each iNod System component will be utilized only to the extent and use limits, defined in the Investigator Brochure. Multiple (a minimum of 4) iNod Ultrasound Catheters and (a minimum of 4) iNod Biopsy Needles are to be available at the commencement of a study procedure.

All iNod System components utilized during a procedure will be recorded, by serial number, to insure device accountability. The model number(s) of the bronchoscope(s) being utilized will also be captured.

The following procedural data will be captured:

- Timing of the total duration of the case, from initial introduction of the bronchoscope to final removal of bronchoscope
- Each iNod Maneuver will be timed from introduction of the iNod Biopsy Needle catheter, pre-loaded with the iNod Ultrasound Catheter, through the removal of the iNod Biopsy Needle.
- Intra-procedural Attributes of the target lesion(s) will be recorded:
 - Location of target lesion (e.g., RB¹, RB², RB³, etc.)
 - Assessment of concentric lesion vs. eccentric lesion
 - Assessment for positive bronchus sign

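### Candidates are selected by the operator and withdrawals before iNod use are uncounted, so the success rate may reflect a favorable lesion mix; the bias-control section addresses neither point

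*SAP*

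**What the plan says.** **Selection.** Protocol 8.2 states: "Potential study candidates will be selected based on the investigator's review of subject referrals". The review covers medical history and a chest CT taken within 6 weeks, and all subjects are the investigators' own patients. Under Protocol 8.5 the investigator inspects all lobes and must "confirm that there are no contraindications to continue with the iNod System procedure". Protocol 9.1.1 and SAP 2.1.2 put the number of bronchoscopists at 2 to 3.

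**Withdrawal.** Protocol 7.2 states: "Reasons for withdrawal include physician discretion", followed by withdrawal of consent, loss to follow-up and death. It adds: "Subjects withdrawn prior to undergoing the diagnostic procedure with the iNod System will not count toward" the center's limit of 10. Reasons for withdrawal must be reported and every enrolled subject accounted for.

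**Enrollment and caps.** Protocol 7.1 puts the point of enrollment at signature of the consent form. Protocol 5, 9.1.1 and 9.2.3 limit enrollment to 10 per center; 9.1.1 also caps it at 30 overall.

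**Bias control.** Protocol 9.2.2 and SAP 3.3 carry the same text: "All subjects who have met the inclusion/exclusion criteria and have signed the ICF will be eligible for enrollment in the study", followed by data review and query resolution.

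**Denominator.** Protocol 9.1.1 divides by lesions in which iNod was attempted. SAP 2.1.3 and 6.3.4 divide by per-protocol patients, meaning those from whom a specimen was obtained.

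**The concern.** The bias-control sentence controls nothing about selection. It makes subjects who have signed eligible for enrollment, although under Protocol 7.1 signing already is enrollment. The rest of the section concerns data quality.

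This matters because the protocol itself expects results to depend on the lesion. Its Introduction says of flexible bronchoscopy in general: "The diagnostic yield with FB varies with lesion size and location", and that a bronchus sign on CT improves the success of transbronchial sampling. The eligible range, 1 to 7 cm, is wide. With 2 to 3 operators filling 5 to 10 places each from their own referrals, the treated lesions could differ from the eligible ones.

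A second filter can act after consent. A subject withdrawn before iNod use leaves the primary denominator and frees a slot. The headline rate would not show either filter. It may also be read out of context, since informal interim looks for abstracts are allowed (SAP 4.2) and results will be submitted for publication (Protocol 21).

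**Working it through.** **1. The plan's own figure.** Three centers × 10 subjects = 30, which reproduces the overall cap in Protocol 9.1.1.

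**2. The non-counting rule against the caps.** Enrollment is consent signature. If each of three centers treats 10 and has one withdrawal before iNod use, enrollment is 3 × (10 + 1) = 33. Protocol 7.2 allows this, but it exceeds 30 overall and 10 per center under Protocol 5, 9.1.1 and 9.2.3. The passages need reconciling.

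**3. Where a subject withdrawn before iNod use appears.**

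| Place | Included? |
|---|---|
| ITT cohort (SAP 3.2.1, 6.3.1) | Yes |
| Center limit (Protocol 7.2) | No |
| Primary denominator, Protocol 9.1.1 | No, iNod not attempted |
| Primary denominator, SAP 2.1.3 and 6.3.4 | No, no specimen |
| Disposition table (SAP 4.6.3) | Presumably, but no such category and no reasons are named |

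An eligible patient who was never approached appears nowhere. The SAP's Screening Form is used in 6.3.3 to read the eligibility answer of subjects already in the per-protocol cohort; nothing says it is kept for patients not approached.

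**4. Illustration of lesion mix.** The documents give no success rates or mixes, so every input here is assumed. With share m of easy lesions, the expected rate is m × p_easy + (1 − m) × p_hard.

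| p_easy / p_hard | m = 20% | m = 50% | m = 80% |
|---|---|---|---|
| 90% / 60% | 0.18 + 0.48 = 66% | 0.45 + 0.30 = 75% | 0.72 + 0.12 = 84% |
| 90% / 50% | 0.18 + 0.40 = 58% | 0.45 + 0.25 = 70% | 0.72 + 0.10 = 82% |

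Device performance within lesion type is fixed in each row. Relative to a 50/50 pool, the shift is +9 or +12 points for an easy tilt, the same size downward for a hard tilt, and zero with no selection.

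**5. Illustration of withdrawals before iNod use.** Assume 24 successes in 30 treated: 80.0%, exact 95% CI 61.4 to 92.3%. Let w further subjects be withdrawn before iNod use and their slots refilled. The reported rate stays at 80.0%. The bounds over all 30 + w are 24/(30 + w), if every one would have failed, and (24 + w)/(30 + w), if every one would have succeeded.

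| w | Lower bound (exact 95% CI) | Upper bound |
|---|---|---|
| 3 | 24/33 = 72.7% (54.5 to 86.7) | 27/33 = 81.8% |
| 6 | 24/36 = 66.7% (49.0 to 81.4) | 30/36 = 83.3% |
| 10 | 24/40 = 60.0% (43.3 to 75.1) | 34/40 = 85.0% |

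The outcome of a subject in whom iNod was never used is unknown, so only the bounds are available.

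**The case against.** The other side has a good deal of the text in its favor.

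- **The enrolled mix will be visible.** Size, location and solidity are recorded at baseline (Protocol 8.4), and concentric or eccentric position and bronchus sign during the procedure (8.5). Baseline data are summarized (SAP 4.6.1). This stands, so it would be wrong to infer that no reader could detect a tilted sample. What stays unseen is the eligible pool to compare it with. A subject withdrawn before the procedure may also lack the attributes recorded during it.
- **Losses after consent are documented.** They stay in ITT and reasons must be reported. This stands in part, because the planned disposition table does not single out subjects in whom iNod was never introduced.
- **Replacement is not stated.** A reader might infer that operators discard difficult cases and replace them. The text says only that such subjects do not count toward 10; refilling is a consequence that the rule permits. Physician discretion stands in a general list of reasons and is not tied to that moment, and checking for contraindications is no license to drop hard lesions.
- **An unreachable lesion is not a withdrawal.** Protocol 8.5 sends it to salvage, and Protocol 9.1.1 keeps it in the denominator as an attempt. That the SAP's per-protocol rule drops attempts without a specimen is a separate matter.
- **The study is descriptive.** It has no hypothesis and promises no representative sample; the sample-size text claims only greater potential to evaluate a range of lesions. It would overreach to say that this rationale fails.
- **The illustrated shifts of 9 to 12 points lie inside the exact interval for 24/30.** True, but that interval expresses sampling error and does not cover selection.

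**Conclusion.** The point holds as a limit on generalizability. Selection by the operator, with no consecutive-offer rule and no log, and uncounted withdrawals before iNod use both let the treated sample differ from the eligible pool, and the bias-control section addresses neither. The success rate may therefore reflect a favorable lesion mix.

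The documents do not show that it will. They give no screening, withdrawal or success rates, so neither direction nor size can be derived. The 9- and 12-point shifts rest wholly on assumed success rates and mixes, and the 72.7% lower bound against a reported 80.0% rests on assumed counts and on treating all three withdrawn subjects as failures. No planned test is invalidated, because none is planned. The case for acting is that the remedy is cheap and that a record of patients not approached cannot be rebuilt reliably afterwards.

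**What to change.** 1. **Protocol 8.2:** offer the study to consecutive eligible patients at each center and keep a prospective screening log with CT size, location, CT bronchus sign, and the reason a patient was not approached or declined.
2. **SAP 4.6.3:** add a flow table (eligible, consented, bronchoscope introduced, iNod introduced) with the reason for each loss, separating contraindications from physician discretion.
3. **Protocol 9.2.2 and SAP 3.3:** refer to these two measures in place of the eligibility sentence.
4. **Optional, beside the primary rate:** show successes over all subjects in whom the bronchoscope was introduced, labeled as a lower bound. It counts stops for true contraindications against iNod, so it should not replace the primary rate.
5. **Protocol 7.2:** reconcile the non-counting rule with the caps in Protocol 5, 9.1.1 and 9.2.3, stating whether they apply to consented subjects or to those who undergo the iNod procedure.

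The cost is a short site log, one table, some coordinator time and possibly slower enrollment.

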3.4 Number of Subjects per Investigative Site

Each investigative site is expected to enroll 5 to 10 patients.

4 ADDITIONAL DATA ANALYSES

4.1 Secondary Endpoints

1. Occurrence and severity of Adverse Events related to the iNod System biopsy procedures, as well as Adverse Events related to any subsequent Radial EBUS-guided salvage procedures.
2. Proportion of lesions visualized during iNod Maneuvers

Study Reference number E7113

3. Proportion of lesions accessed where iNod Biopsy Needles were deployed in the target lesion during study maneuvers
4. Proportion of iNod maneuvers that acquire specimens of cellular matter for cytology

4.2 Interim Analyses

No formal interim analyses are planned for the iNod Feasibility Study for the purpose of stopping the study early for declaring effectiveness or for futility. Informal interim analysis may be conducted for the purpose of submissions of abstracts to major professional meetings.

4.3 Subgroup Analyses

No subgroup analysis is planned.

4.4 Justification of Pooling

The analyses will be presented using data pooled across centers as well as by center for the primary endpoint. If deemed appropriate, stratified and multivariate analysis techniques, including Chi-square test or logistic regression, will be used to assess differences between study centers to justify pooling data across centers.

4.5 Multivariable Analyses

No multivariable analyses are planned for this study.

4.6 Other Analyses

4.6.1 Baseline Characteristics

Baseline data will be summarized to assess subject demographics, clinical history, risk factors, and pre-procedure characteristics. Data will be summarized as described in Section 3.1.

4.6.2 Post-Procedure Endpoints

Post-procedure information will be collected at regularly scheduled follow-up examinations as detailed in the clinical trial schedule in the protocol. Data will be summarized as described in Section 3.1.

4.6.3 Subject Disposition

Subject disposition (e.g., number completing the study, number lost-to-follow-up) will be summarized with frequency tables for each visit.

4.7 Changes to Planned Analyses

Any changes to the planned statistical analyses made prior to performing the analyses will be documented in an amended statistical analysis plan approved before performing the analyses. Changes to the planned statistical methods not documented in an updated statistical plan will be documented in the clinical study report along with a reason for the deviation.

5 VALIDATION

All clinical data reports generated per this plan will be validated per 90702587, Global WI: Clinical Data Reporting Validation.

Boston Scientific
iNod Feasibility SAP
91154618 Rev/Ver AA
Page 7 of 11

6 PROGRAMMING CONSIDERATIONS

6.1 Statistical Software

Statistical data review will be performed by the sponsor. Statistical analyses will be performed using SAS System software, version 9.2 or later (Copyright © 2000 SAS Institute Inc., [name], USA. All rights reserved).

6.2 Format of Output

Results of analysis will be output programmatically to Word documents from SAS with no manual intervention. All output for the final statistical report will be in the form of a Word document containing tables, figures, graphs, and listings, as appropriate.

